Following our current usability testing (anticipated completion: August 2018), we will employ a two-site study to test the MASS application in a total of 30 persons (we will recruit up to 50 people to account for attrition, ending up with complete data on 15 persons per site) with schizophrenia or schizoaffective disorder over a 60-day period. We will measure social functioning at baseline, intervention termination, and 90-day post-intervention follow-up using the Social Functioning Scale (SFS) and the Quality of Life Scale (QLS). Social cognition and preference for personal space will be measured with the Stop Distance Paradigm. We will also measure symptoms and cognitive function with the Brief Psychiatric Rating Scale (BPRS) or the Wide Range Achievement Test (WRAT), the Clinical Assessment Interview for Negative Symptoms (CAINS), Penn Emotion Recognition Task (ER-40) and the Brief Assessment of Cognition Schizophrenia (BACS). Self-report measures to assess theory of motivation and social skills will also be administered. Self-report measures and the ER-40 will be administered through Qualtrics. Demographic information will be collected through a custom questionnaire and the Structured Clinical Interview for DSM-5 [SCID-5]). Participant satisfaction questionnaire will also be administered at termination and a subset of the satisfaction questions will be administered at follow up.

Procedures

Baseline Assessment. After providing informed consent, participants will complete diagnostic and clinical evaluations at the Center for Psychiatric Rehabilitation or in the [name] or [name] laboratories. The assessment procedures will involve a total of 4 hours for the completion of clinical interviews, demographics questionnaires, cognitive/behavioral tests, and community functioning measures, conducted over 1-2 days as needed by participants. At the conclusion of the assessment, the participant will be issued a mobile phone and trained on its use. They will identify a social goal and work with study staff to lay out sub-goals and steps necessary to achieve them—this goal will be programmed into the mobile app based on a pre-defined set of available goal prototypes. Participants will be oriented to all application components during this visit. They will also be given instructions to watch the social skill video clips within the app.

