Mobile Intervention. Research assistants will call participants the day after the initial meeting and will provide instruction on watching 4 brief summaries of the social skills training video clips (each video summary is approximately 10 minutes in length). They will then be called 1-2 days later to check in on video watching and will be instructed to watch the second video summary. 1-2 days later they will receive another call to again check in and will be instructed to watch the final summary. Call frequency will be based on participant preference. We will also provide follow up calls based on adherence to EMA reports (ascertained by logging onto the mobile app's researcher portal online) throughout the course of the 60-day intervention trial.

Participants will always have the option of calling our laboratory to discuss any issues with the phone or mobile intervention.

Use of the MASS application over the 2-month intervention period will involve interaction with social goal-related content based on pre-programmed notifications that alert the participant 2 times per day, 7 days per week. These notifications involve reminders of the identified social goal and associated steps—once in the morning and once in the evening. All notifications expire after a period of one hour.

If the phone is lost, that we will do whatever we can to replace the phone. If the phone cannot be replaced (e.g., due to budget availability), we will notify the consumer that their study participation will be discontinued. Data collected up to the point of the phone being lost will be used for analysis.

Follow-Up Assessments. Participants will return again after the 60-day intervention period for a 2-hour follow-up session to complete outcome measures. They will again complete an in-person assessment 90 days following intervention termination. Audio and video recordings of participants may also be collected during interviews and assessments for training purposes and to verify records collected during the study. Recordings will be kept for 7 years per Boston University (BU) Record Retention Policy.

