Quality of Life Scale (QLS)	Social Functioning	B, T, F
Brief Psychiatric Rating Scale	Psychiatric Symptoms	B, T, F
(BPRS)		
Clinical Assessment Interview for	Psychiatric Symptoms	B, T, F
Negative Symptoms (CAINS)		
Stop Distance Paradigm	Social Cognition	B, T, F
Penn Emotion Recognition Task	Social Cognition	В
(ER-40)		
Brief Assessment of Cognition	Neurocognition	В
Schizophrenia (BACS)		
Wide Range Achievement Test	Neurocognition	F
(WRAT)		
Self-reports: Implicit Theory of	Social Cognition	В
Motivation (TOM), Implicit		
Theory of Social Skills (TOSS)		
Self-Reports: Birchwood Social	Social Functioning	B, T, F
Functioning Scale		
Satisfaction Questionnaire.	N/A	T, F
Demographics	N/A	В

^{*}B = Baseline; T = Termination; F = Follow-up

Analyses

Primary analyses will examine changes in social functioning across the study period using multivariate models accounting for covariates of interest (e.g., demographics, cognition). This mobile application is both an intervention and assessment tool. Thus, during the intervention we will be able to measure additional targets of interest, social motivation and functioning, using the EMA reports of positive affect in anticipation of social interactions, as well as reports of actual engagement in interactions, throughout the intervention period.

This study is a within-subject experimental design. Consistent with an experimental therapeutics approach, our primary goal is to identify change within the treatment targets (social anticipatory pleasure and presence of social interaction). Accounting for up to 20% attrition, we aim to recruit 50 participants, allowing for 20 participants to drop out/not meet criteria and still leave adequate power for primary analyses. Our primary aims are to pilot test the intervention to determine feasibility and efficacy in the treatment targets (social skills and motivation) and outcome (social functioning).

SECTION M: RISKS

Describe any expected risks to subjects. Consider physical, psychological, social, political, legal, economic, or other risks that are related to the study.

There are some risks associated with participation in the study. The primary risks involve loss of confidentiality associated with pilot testing of the mobile application. It is also possible that some participants may feel some frustration when participating in the MASS application. Participants may also feel discomfort answering questions about their health in the clinical assessments.

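### A lost phone that cannot be replaced ends study participation, so termination and 90-day SFS and QLS that do not need the phone go uncollected

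*Combined protocol and SAP*

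**What the plan says.** The rule is in Section L, Mobile Intervention. Staff first try to supply another phone: "If the phone is lost, that we will do whatever we can to replace the phone". If they cannot, for example because of budget, "we will notify the consumer that their study participation will be discontinued". On the data of such a person it says: "Data collected up to the point of the phone being lost will be used for analysis".

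The outcome schedule is separate from the app:

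- The Measures table in Section L lists the SFS and QLS at baseline, termination and follow-up. Section G says social functioning is measured by clinician interview and self-report questionnaire.
- Under Follow-Up Assessments, participants return after day 60 for a two-hour session, and then: "They will again complete an in-person assessment 90 days following intervention termination".
- Under Phase II: "Self-report measures and the ER-40 will be administered through Qualtrics". The same paragraph adds: "Participant satisfaction questionnaire will also be administered at termination", with a subset of its items repeated at follow-up.
- Under Analyses: "Primary analyses will examine changes in social functioning across the study period". Feasibility is also among the primary aims there.
- On numbers, Phase II says: "we will recruit up to 50 people to account for attrition, ending up with complete data on 15 persons per site".

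No other section keeps a person without a phone in the study for outcome assessment.

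**The concern.** Losing the phone ends exposure to the app and stops the momentary reports and GPS data. It does not stop anyone from attending an interview or completing a questionnaire. The rule nevertheless ends participation in the study, so an interruption of the intervention becomes missing outcome data. A loss before the termination visit costs both post-baseline SFS and QLS assessments and the satisfaction questionnaire, which bears on the feasibility aim. If the rule also applied after termination, only the 90-day assessment would be lost.

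This matters because the design is a single group measured before and after, so no control arm offsets selective loss of visits. Recruiting until each site has 15 complete cases restores the sample size but does not bring back the people removed. If they would have changed differently from those who stay, the estimated mean change no longer describes everyone who was issued a phone. The protocol gives no basis for saying which way it would move.

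**Working it through.** **1. Does the rule remove data that could be collected?**

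| Item | Needs the study phone? | Where |
|---|---|---|
| Momentary (EMA) reports, GPS, app use | Yes | Section L, MASS Application and Analyses |
| SFS, QLS | No: interview or questionnaire at an attended visit | Sections G and L |
| Self-reports | No: run through Qualtrics | Section L, Phase II |
| Satisfaction questionnaire | Nothing ties it to the phone | Section L, Phase II and Measures |

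The rule stops all four rows, while the lost phone accounts only for the first. Section M lets participants turn the app off at any time without saying that this ends participation, so the protocol tolerates non-use of the app elsewhere.

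**2. How large could the effect be?** The protocol states no phone-loss rate, SD, visit correlation or significance level. All of the following are assumptions:

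- Target: mean change in everyone issued a phone.
- Analysed n = 30, with removed people replaced. So k removals mean 30 + k starters, and the removed fraction is p = k/(30 + k). Other dropout is unrelated to change.
- k = 1, 2 or 4, giving p = 1/31 = 3.2%, 2/32 = 6.3%, 4/34 = 11.8%.
- d, the difference in mean change between stayers and those removed, is 0.2, 0.5 or 0.8 outcome SD.
- Correlation between visits r = 0.6.

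Shift in the estimated mean change = p × d:

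- smallest: 0.2 × 1/31 = 0.006 SD
- two losses, largest: 0.8 × 2/32 = 0.050 SD
- four losses, largest: 0.8 × 4/34 = 0.094 SD

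Variance of change = 2(1 − 0.6) = 0.8, so the standard error is √(0.8/30) = 0.163 SD. The largest shift is 0.094/0.163 = 0.58 standard errors.

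**3. False-positive rate.** This is the rejection rate when the true mean change over all starters is zero, for a two-sided 5% one-sample t-test (exact noncentral t, 29 df, variance among stayers 0.8 − p(1 − p)d²):

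| Losses k | d = 0.2 | d = 0.5 | d = 0.8 |
|---|---|---|---|
| 1 | 5.0% | 5.1% | 5.3% |
| 2 | 5.1% | 5.4% | 6.1% |
| 4 | 5.2% | 6.45% | 9.0% |

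The worst cell (k = 4, d = 0.8) is 8.1% at r = 0.5 and 13.9% at r = 0.8. At r = 0.8 the SD of change is √0.4 = 0.632, so d = 0.8 is 0.8/0.632 = 1.26 SD of change, which is extreme.

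**4. What would inviting people back achieve?** If a fraction a of those removed attend, the shift is (1 − a)p(1 − p)d / (1 − (1 − a)p). For k = 4, d = 0.8:

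| Attend (a) | Shift (SD) | Simulated false-positive rate |
|---|---|---|
| 0 | 0.094 | 9.1% |
| 0.5 | 0.044 | 5.9% |
| 0.8 | 0.017 | 5.3% |
| 1 | 0 | not run |

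The simulation used 200,000 trials with analysed n = 30 and r = 0.6.

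**The case against.** The strongest reply is that this hardly matters. The rule needs two events, a lost phone and a failed replacement, and the protocol gives no rate for either. With one or two such people, the shift is well below one standard error. The larger error rates need four irreplaceable losses and a 0.8 SD difference together. All of that stands, and it is why the point is minor.

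Second, the bias exists only if the target is everyone issued a phone. Section L, Analyses, also calls change in the treatment targets (social anticipatory pleasure and presence of social interaction) its primary goal. The momentary reports of these come through the app and stop with the phone whatever the visit rule. If the target were only people who kept the app, these removals would not produce the computed shift. That is fair, but the same section makes change in social functioning the subject of the primary analyses, and the protocol does not restrict it to people who kept the app.

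Third, the text does not literally cancel the later visits, and the sentence sits in the intervention paragraph. It may have been meant to end app use only. In that case it still needs the same correction, because staff will act on the words as written. The placement does make it doubtful that a loss after termination would trigger the rule.

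Fourth, the plan is for multivariate models with covariates, not a one-sample t-test, so the error rates above are illustrative. People without the study phone may also be harder to reach, so full return should not be assumed; the partial-attendance figures allow for this.

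**Conclusion.** The concern holds and is minor. As written, the rule ends study participation when only app use has become impossible, and it discards post-baseline primary-outcome data that could be collected at visits already planned. The reading of the text is firm. The size is not, because loss rate, difference and correlation are all assumed. For one or two irreplaceable losses at r = 0.6, the false-positive rate is 5.0% to 6.1%; for four it is 5.2% to 9.0%. No direction of bias can be claimed. The case for changing the rule is that the loss is avoidable and cheap to prevent, not that it would probably alter the pilot's conclusion.

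**What to change.** In Section L, Mobile Intervention, replace the discontinuation clause with wording such as: *app use and EMA will end, but the participant will still be invited to the termination and 90-day assessments unless they withdraw consent.* Amend the data-use sentence that follows it to match. In addition:

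- Record the date and reason that app use ended.
- Include these participants' termination and 90-day data in the analysis of change in social functioning, with an analysis of those who kept the app as a sensitivity analysis.
- Keep recruiting to 15 complete cases per site, and state whether someone who returns without EMA data counts as complete.

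The cost is one protocol sentence with its data-use sentence, matching consent wording and an IRB modification. Section O pays $15 per hour for two hours of follow-up without saying whether that covers both visits or each. This gives $30 or $60 per person; the two-hour termination session in Section L fits $60 better. For one to four people the range is $30 to 4 × $60 = $240, plus interviewer time. The trade-off is that some analysed participants will have had only partial app exposure, so the main result describes everyone issued a phone.

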Schizophrenia is a severe mental illness that affects millions of people worldwide. The illness is often associated with social impairments, including limitations in verbal and non-verbal behavior, initiating conversations, and social motivation. People with schizophrenia often report a desire to socialize but expend less effort in the actual behavior and set fewer socially-related goals than others. While diminished social motivation is not fully understood, past research suggests a reduced ability to connect past, pleasurable experiences with current states, resulting in reduced effort for social connection in people with schizophrenia. Because this reduced effort for social connection may cause people with schizophrenia to have difficulty obtaining relationships they desire, it is important to focus on factors that are modifiable, such as social skills and motivational deficits. Interventions that target these impairments usually take place at mental health clinics, but there is a growing recognition that people with schizophrenia need assistance with these skills outside of a clinical setting.

Findings from an ongoing study (i.e., Aims 1 and 2 of the larger grant; (NIMH# R21MH111501-01, IRB protocol #4394) will inform development of a pilot intervention study examining the impact of this mobile application on social functioning over time. We will employ a two-site study to test the application in a group of 30 persons with schizophrenia over a 60-day period. We will measure social functioning at baseline, intervention termination, and 90-day follow-up using clinician administered interviews and self-report questionnaires. We hypothesize that levels of social functioning will increase significantly from baseline to post-intervention and follow-up, and that these increases will be accompanied by increased self-reported social motivation using periodic measures incorporated into the mobile application.

SECTION H: RESEARCH METHODS AND ACTIVITIES (Check all that apply)

\boxtimes	Collection of audio, video, digital, or image recordings
	Biological samples → Complete Biological Samples Form:
	http://www.bu.edu/researchsupport/compliance/human-subjects/
	Examples: blood, hair, cheek swab, urine, tears, saliva, etc.
	Collection of data that may be sensitive and if disclosed could put subjects at risk for
	legal or social harms.
	Examples: Illegal behaviors, HIV status, psychiatric illness, information related to
	sexual behaviors, etc.

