Describe the plan to minimize risks. Include in the description the availability of any medical or psychological resources.

Research staff will receive guidelines and supervision about how to respond to consumers' distress that may arise (albeit rarely) during the pilot testing (during phone or in-person checkins). A number of options are available for dealing with such distress, including discussing the distress with the consumer, practicing a relaxation exercise (e.g., relaxed breathing), taking a break from app use, evaluating the cause of the distress and addressing it, or meeting with their clinician. These strategies have proved useful for our active mobile assessment and intervention studies.

To address possible discomfort that might arise during interviews, all consumers will be informed that information obtained during assessments is confidential and that they can choose not to answer certain questions if they prefer not to. If consumers feel uncomfortable they will be encouraged to take a break and continue the assessment later, or will be offered to stop the interview. The research interviewer may also offer to call the consumer's case manager, another staff member, or concerned others (such as a close friend) to make sure the consumer has someone to talk to about the assessment. In our prior research on consumers over the past several decades, few consumers have expressed discomfort from participating in interviews and assessments. In regards to interviews, we will remind all participants before and during the sessions that all information shared in these sessions should be held in the strictest confidence.

Participants will be clearly informed that they may choose not to participate in any of the tasks should they experience any discomfort at any time. If a participant chooses to discontinue participation at any time, he or she will still receive payment for his or her participation. Participants will have the option to turn off the app at any time—they will be informed of this option verbally and on the consent form, and shown how to do it prior to initiating the study.

SECTION N: BENEFITS

Describe the potential benefits to subjects related to the study. State if there are no direct benefits.

NOTE: Compensation and/or course credit are not considered benefits.

There are no known direct benefits related to participation in the study.

Describe the potential benefits to society and/or others related to the study

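### Does planning for 30 people with complete data out of 50 recruited leave the handling of drop-outs undefined in a way that needs a change?

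*Combined protocol and SAP*

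**What the plan says.** Section L of the combined protocol and SAP gives the numbers twice. Under Phase II: Pilot Testing, "we will recruit up to 50 people to account for attrition, ending up with complete data on 15 persons per site". Under Analyses, it allows for up to 20% attrition and a recruitment target of 50, "allowing for 20 participants to drop out/not meet criteria and still leave adequate power for primary analyses".

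Only one kind of early stop has a data rule. Under Mobile Intervention, a participant whose lost phone cannot be replaced is discontinued, and "Data collected up to the point of the phone being lost will be used for analysis". For people who stop by choice, Section M deals with payment and not with use of their data. Section P lets participants have data excluded from the study.

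The Analyses text names multivariate models of change in social functioning with covariates, and EMA (in-app) reports collected through the 60 days. It defines no analysis set, missing-data method or retention denominator. It also states: "Our primary aims are to pilot test the intervention to determine feasibility and efficacy".

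**The concern.** One allowance of 20 covers two groups that an analysis treats differently. People found ineligible after consent never start the app and belong in no effect estimate or retention rate. Drop-outs do start it and belong in both. If the 30 with complete data were the analysis set, two kinds of information would be lost. One is the baseline-to-termination change of anyone who missed only the 90-day visit. The other is the EMA reports of anyone who stopped early. The lost-phone rule would then look like an isolated exception.

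The design makes this worth asking. There is no control arm, and the Section G hypothesis is directional: "We hypothesize that levels of social functioning will increase significantly from baseline to post-intervention and follow-up". Section M supplies a possible reason for selective loss, since "some participants may feel some frustration when participating in the MASS application" and "Participants will have the option to turn off the app at any time". If people who gain less leave more often, completers would show more improvement than the whole group did. The feasibility result would also depend on which denominator was chosen.

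**Working it through.** **The plan's own figure.** Inputs from Section L: 50 recruited, 20 lost, 15 complete per site. 50 − 20 = 30 = 2 × 15, so the totals agree. The pooled loss is 20/50 = 40%. This fits with 20% attrition only because ineligible people are in the same allowance: 30/0.80 = 37.5, or 38 starters, which leaves 8 drop-outs and 12 ineligible. If the 20% is instead taken of 50, there are 10 drop-outs and 40 starters.

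**Retention with 30 completers (exact 95% CI).**

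| Denominator | Retention | 95% CI |
|---|---|---|
| 38 starters | 30/38 = 79% | 63–90% |
| 40 starters | 30/40 = 75% | 59–87% |
| 50 consented | 30/50 = 60% | 45–74% |

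The 60% figure needs screen failures in the denominator, which the protocol does not propose.

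**Possible bias in a completers-only analysis.** Every input here is an assumption, because the documents give no drop-out mechanism, SD or significance level. Suppose the true mean change over all starters is zero and drop-outs do worse than completers by a gap *g*, in SDs of change. Then the completer mean = *g* × drop-outs/starters. For a paired t test on 30 people, the chance of a false significant increase is P(T > 2.045), where T is noncentral t with 29 df and noncentrality = mean × √30. The nominal value is 2.5%.

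| Gap | Completer mean (38 / 40 starters) | False positive (38 / 40) |
|---|---|---|
| 0.25 SD | 0.053 / 0.063 | 4.6% / 5.2% |
| 0.5 SD | 0.105 / 0.125 | 8.0% / 9.7% |
| 1.0 SD | 0.211 / 0.250 | 19.9% / 26.3% |

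At a gap of zero there is no bias.

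**The direction is not fixed.** Simulate 40 starters with 10 drop-outs who leave more often at low baseline, a true change of 0.30 SD of the score, and baseline–follow-up correlation 0.4 / 0.6 / 0.8. Completers then show 0.12 / 0.18 / 0.24 SD, which understates the effect. A regression-based estimate that keeps drop-outs' baselines gives 0.30 SD in each case.

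**Would a written rule remove the inflated error?** It depends on whether drop-outs have a post-baseline score.

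- *They have none.* Filling in zero change for *s* − 30 people multiplies the mean by 30/*s*. Its standard error goes from about σ/√30 to about σ√30/*s*, which is also a factor of 30/*s*. The test statistic hardly moves. In simulation, false positives with zero-filling are 8.0% / 9.7% at a gap of 0.5 SD and 20% / 26% at 1.0 SD, essentially the same as for completers.
- *They attended termination and missed only follow-up.* With loss more likely after a poor change (log-odds 0.5 per SD), completers-only analysis of baseline-to-termination change gives +0.11 / +0.13 SD and 10% / 11% false positives. Using everyone with both visits gives 0.00 SD and 2–3%.

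**Passages side by side.** The Analyses sentence explains why 50 are recruited, and the Phase II sentence gives a target for complete data. Neither says that anyone with partial data is left out. The Mobile Intervention sentence is the only one that speaks to analysing partial data, and it includes them. The three can all hold at once.

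**The case for a change.** The strongest case for a change is that the gap is real and cheap to close. No readable section says which discontinued participants are analysed, and efficacy and feasibility are both named as primary aims. Drop-outs are also not empty records. Someone who misses only the last visit has an observed baseline-to-termination change, and EMA reports on the treatment targets accrue until a person stops. Section S holds the analyses until all data are collected, so a rule could be fixed before results are seen, with no added visits or participants.

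Much of this stands. The definitions are missing, and discarding observed changes can bias the result, as the termination-visit simulation shows. But the plan does not tell anyone to discard them. Multivariate models of change over three visits can be fitted to all available data, and the lost-phone rule already points that way. Turning the app off also need not mean missing an assessment.

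Where bias would be hardest to deal with, among people with no post-baseline SFS or QLS score, the zero-change check leaves the false-positive rate where it was. A blanket rule to use data from every discontinued participant would also collide with the Section P option to exclude data unless that were carved out.

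**Conclusion.** No change to the plan follows. The sample-size sentences and the lost-phone rule do not contradict each other, and no stated rule produces a wrong result. What is missing is detail that analysts fill sensibly: report people found ineligible apart from drop-outs, use the available data of those who started the app unless a participant has asked for exclusion, and give retention with its counts.

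For 30 completers the retention figure lies between 60% and 79% on the denominators considered, and publishing the numbers consented, issued a phone and assessed at each visit removes the ambiguity. The effect estimate can change with the analysis set, but neither size nor direction can be read from the documents. The 5–26% false-positive range requires a completers-only analysis that the plan does not prescribe, drop-outs who do worse by 0.25 to 1.0 SD, and a paired t test in place of the planned models. This conclusion rests on reading the 30 as a recruitment target; it would differ if the protocol restricted the primary analyses to completers, and no readable section does.
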